3.6.3. Data Management

For all phases, patient identifiers will be removed and a separate linking file will be kept in a password-protected computer with access only by the study staff to allow for data quality assessments of the EMR. All data will be kept in a password-protected database.

Pre-PDC Phase One:

After collection of the completed data forms, all information will be uploaded into a password-protected database.

Post-PDC Phase Two:

Data will be extracted from the EMR system and exported into Stata for statistical analysis. All participants will be assigned a study ID. Any additional data that is not in the EMR will be entered from paper-based patient files into a database for data management and cleaning. Additional paper-based data extracted from patient charts and entered into KoboCollect will be merged into the EMR databased by linking study IDs (Aim 3). Data on PDC patients for Aim 4

will be extracted from the EMR and/or additional patient records and data from household interviews will be collected using KoboCollect and securely stored with an SSC connection and password protection. Data on PDC patients will be appended to de-identified comparison datasets for study aims 4a and 4b for analysis.

Expanding-PDC Phase Three:

Data will be extracted from the EMR system and exported into Stata for statistical analysis. All participants will be assigned a study ID. Any additional data that is not in the EMR will be entered from paper-based patient files or gathered through interviews into KoboCollect, or other comparable software, database for data management and cleaning. Additional paper-based data extracted from patient charts and entered into KoboCollect will be merged into the EMR databased by linking study IDs. Cost-data will also be entered into a KoboCollect, or other comparable software, database for data management and cleaning. Qualitative data will be collected using audiorecorders. Kinyarwanda transcripts of recorded interviews and focus groups will be translated into English for analysis.

3.6.4. Analysis Plan

Pre-PDC Phase One:

Aim 1: Describe the baseline outcomes of a selected sample of infants discharged from a rural hospital neonatal unit.

Analysis Plan:

The primary analysis will be a univariate analysis describing the proportion of children discharged from the neonatal unit with developmental delay at two years of age. This is the primary outcome of the study and will provide vital data regarding neonatal outcomes at two years after discharge from neonatal unit. Proportions will be calculated for categorical variables and means with standard deviations will be calculated for continuous variables.

Categorical variables include: sex, sector, alive/dead, malnutrition (yes/no), malnutrition category (low, moderate, severe), medical comorbidities (anemia, respiratory disease,

possible hydrocephalus, and feeding difficulty), ubudehe category (measure of economic status), and education level of the caregiver.

Continuous variables are birth weight, gestational age, age at the time of data collection, and household size.

Aim 2: Identify specific patient-level predictors of developmental delay

Analysis Plan:

We hypothesize that birth weight (< 1kg, 1-1.5kg, 1.5-<2kg, \geq 2 kg), gestational age (<32 weeks, 32-36 weeks, \geq 37 weeks), and malnutrition (yes/no) will be significantly associated with developmental delay in bivariate and multivariable analyses.

Chi square test will be performed to test for associations between these categorical variables and the primary outcome (developmental delay). A multivariable logistic regression model will be created to identify predictors of developmental delay controlling for potential covariates using the same list of descriptive variables. However, this analysis will only be performed if there are a sufficient number of children with the primary outcome to have sufficient power to detect predictors.

Post-PDC Phase Two:

Aim 3: Describe the PDC and patients enrolled in the PDC

Analysis Plan:

Demographic characteristics, services provided to patients, and clinical, nutritional and developmental outcomes will be described using descriptive statistics. For continuous variables, mean and standard deviations will be reported unless the distribution is not normal and then medians and inter-quartile range will be reported. Frequencies and percentages will be reported for categorical variables.

Aim 4a: Compare developmental, medical, and nutritional outcomes of children who were enrolled in the PDC to medically vulnerable children who did not receive PDC support (from Baseline Phase One)

Analysis Plan:

We will use bivariate analyses to compare the outcomes of infants who received PDC services with those who did not receive these services (the baseline data from Phase One). Developmental delay will be scored as a binary outcome looking at the proportion of children who failed one or more ASQ-3 domain at baseline to the proportion of children enrolled in PDC who failed one or more ASQ-3 domain. We will use a chi square test or fishers exact test look for significant differences in the number of children with developmental delay between children who received PDC services and those who did not. Chi squared or fishers exact tests will also be used to assess for differences in nutritional outcomes (normal, moderate, and severe malnutrition indicators) and medical outcomes among the two groups.

If we have sufficient power, we will conduct logistic regression analyses to look at predictors of developmental delay in the sample. Using backwards selection, all variables associated with developmental delay at $p < 0.10$ in bivariate will be included in the full model. We will report Odds Ratio, p-value, and 95% confidence intervals for multivariate analyses.

Aim 4b: Compare developmental, medical, and nutritional outcomes of children who were enrolled in the PDC to a sample of Rwandan children from ten rural sectors across the country.

Analysis Plan:

We will use bivariate analyses to compare the outcomes of infants who received PDC services with a random sample of children from rural communities in Rwanda (a pre-existing dataset). Developmental delay will be scored as a binary outcome looking at the proportion of children who failed one or more ASQ-3 domain in the random sample of Rwandan children from rural areas to the proportion of children enrolled in PDC who failed one or more ASQ-3 domain. We will use a chi square test or fishers exact test look for significant differences in the number of children with developmental delay between children who received PDC services and those who did not. We will use chi squared or fishers exact test to assess for differences in nutritional (normal, moderate, and severe malnutrition indicators) among the two groups. Medical outcomes will not be assessed because the comparison database only collected data on demographics and current

developmental and nutritional status.

Expanding-PDC Phase Three:

Aim 5: Analyses of PDC expansion will be focused on descriptive analyses of process, output and selected outcome measures including, patient outcomes, quality of care, and quality improvement interventions according to defined standards, training and mentorship activities, referral rate, retention, barriers and facilitators to care, patient and provider experiences, and patient health, nutritional, and developmental outcomes. These data will be used to monitor impact of PDC on patient outcomes as well as continuous quality improvement of the model, such as the introduction of the new mHealth application to improve quality of growth monitoring. As appropriate, bivariate and multivariate analyses will be used. Qualitative analysis will use thematic coding.

Aim 5. 1. Descriptive analyses to evaluate the implementation of interventions to promote breastfeeding from as early as day one of life among newborns in the referring hospital neonatal units will focus on analysis of exclusive breastfeeding rates and proportion of newborns requiring formula pre-post quality improvement interventions.

4. Study Limitations

Pre-PDC Phase One:

1. Data is based on caregiver report and therefore subject to recall bias of the caretakers.
2. The high-risk infants who were hospitalized in the neonatal unit were not from one specific sector. The Rwinkwavu Neonatal unit serves as a referral center for the Southern Kayonza district. Each of the sectors within the district may not be environmentally identical. Specifically the availability of food, amount of rain and distance to health centers are factors that could influence the outcomes of the high-risk neonates and therefore could result in residual confounding.
3. The gestational age and birth weight are subject to misclassification.
4. This is cross sectional data, and therefore any associations found are unable to assess causality.
5. Exclusion criteria undiagnosed by register are subject to misclassification.

Post-PDC Phase Two:

1. This study will be a cross-sectional study, and therefore associations may be found, but we will be unable to assess causality.
2. For the Aim 4b comparing PDC participants and UNICEF sample, only similar age groups will be compared; therefore, the number of children may be reduced which might affect the power of the study and its external validity.
3. As this is a secondary dataset analysis, missing values are expected.
4. The gestational age and adjusted age are subject to misclassification due to recall bias.

Expanding-PDC Phase Three:

1. As this is primarily a secondary dataset analysis of routinely collected data, missing values are expected.

5. Ethical Considerations

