3.1. Study description

This study has three phases. In the first phase, descriptive study will investigate at the community level the developmental, medical and nutritional outcomes of infants discharged from the neonatal unit, aged between 12 to 36 months at the time of data collection. In the second phase, the study will assess the services provided to children enrolled in the PDC and compare their outcomes to children from the first phase as well as to an existing random sample of children from an existing database. In the third phase, research will focus on answering questions raised from the initial PDC study aims – including patient and provider experiences, expansion of the PDC model, overall clinic processes, enrolment rates and retention, cost-effectiveness, and longer term outcomes of children enrolled in the PDC to further help refine the PDC model and maximize benefits for children.

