3.4. Study population

Pre-PDC Phase One:

All infants discharged from the Rwinkwavu District Hospital neonatal unit during the designated time period fulfilling the inclusion criteria: children were included if they were discharged between October 2011-October 2013 (prior to PDC implementation).

Post-PDC Phase Two:

All children enrolled in the PDC are eligible. PDC serves children up to age five years with prematurity, low birth weight, birth asphyxia, other perinatal risks, and other developmental delays.

Expanding-PDC Phase Three:

All children and their caregivers enrolled in the PDC clinics in S. Kayonza and Kirehe Districts are eligible. PDC serves children up to age five years with prematurity, low birth weight, birth asphyxia, other perinatal risks such as post CNS infections_cerebral malaria and meningitis, and other developmental delays.

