3.6. Study Procedures

3.6.1. Procedures at enrollment and data collection.

Pre-PDC Phase One:

After consent is obtained, data will be collected using a data collection form and the ASQs from 12 to 36 months of age on an Android tablet. The ASQ is a validated screening tool for child development that has also been translated to Kinyarwanda and validated for local use. The Ages and Stages questionnaire went through a validation process with the publisher to adapt the screening tool to Rwanda. The questionnaire was first translated from English to Kinyarwanda. After translation the questionnaire was field-tested. The questionnaire was then adapted to Rwandan cultural context and underwent field-testing again. The ASQ went through a final adaptation to Rwandan culture and was translated to English. It was then back translated to Kinyarwanda and finally submitted to the publisher for approval. Questions will be in a simple yes/no format and growth parameters of weight, height, head circumference and MUAC will be measured. Questions will be asked about the medical complications and developmental milestones will be assessed using the ASQs per age group. Upon data collection completion, the growth parameters and medical comorbidities will first be entered into the database and then the ASQ will be scored by a study staff. The scoring of the ASQ will be based on the answers of the caregivers. A score will be given to each answer. The ASQ has three possible answers: yes, not yet, or sometimes. At the end of the questionnaire the total score will be tabulated for each of the

five subsections based on a standard scoring methodology. Depending on the score, the questionnaire will be counted as normal or abnormal (developmental delay present).

Developmental delay will be defined as any single domain score that falls within the limits of concern or delay according to the ASQ scoring table at the end of the questionnaire.

Post-PDC Phase Two:

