Patient flow: Group education, individual social worker screening, clinical evaluation including danger sign assessment, nutritional assessment/classification/treatment, developmental screening/therapy, and condition-specific screening and treatment.

Aim 4: Compare developmental, medical, and nutritional outcomes of children who were enrolled in the PDC to other children on the main outcomes of prevalence of developmental delay as measured using the Ages and Stages Questionnaires (ASQ-3) and the prevalence of undernutrition (stunting, wasting, underweight) using anthropometric assessments.

This aim is to describe the clinical, nutritional, and developmental outcomes of vulnerable patients enrolled in PDC in comparison with:

- a. Medically vulnerable infants who did not receive PDC support. This comparison will be made using a cohort of preterm/LBW children who were born in Rwinkwavu District Hospital (RDH) before PDC started with medical, nutritional and developmental outcomes assessed at 12-36 months of age (the dataset from Aim 1).
- b. The general population of rural Rwandan children.² This comparison will be looking at developmental outcomes of children followed in PDC compared to the similar age children from the general population using UNICEF data that was collected in children ages 0-11 months and 24-35 months randomly sampled from ten rural sectors of the country.

Additional variables to be measured include (See Appendix F for data source forms of routinely collected data and Appendix A for household interview forms. All measures used in the household interview were previously used in the two comparison datasets):

- Descriptive characteristics of caregivers.
- Proportion of visits where a nutritional screening was done, danger sign screening was done, and patient had a documented ASQ within the 6 months prior to visit date.

² This existing data set was collected by UNICEF, Harvard School of Public Health, Partners In Health, and the University of Rwanda. [name] and [name] were investigators on both study teams and have access to the data.

- Proportion of children who received nutrition supplement.
- Proportion of currently enrolled children with a visit in the reference quarter whose caregivers have had at least one documented ECD counseling session
- Proportion of children with moderate or severe chronic malnutrition (height/age Z score < 2 or height/age z score < 3) at the last visit.

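### The Phase One primary analysis is labelled a two-year outcome, but the survey measures delay once, at any age from 12 to 36 months, and plans nothing specific to 24 months

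*Combined protocol and SAP*

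**What the plan says.** Section 3.6.4 (Analysis Plan, Aim 1) describes the primary analysis as a univariate one, "describing the proportion of children discharged from the neonatal unit with developmental delay at two years of age". The following sentence calls this the primary outcome and says that it "will provide vital data regarding neonatal outcomes at two years after discharge from neonatal unit". The two sentences use different time origins: birth in the first, discharge in the second.

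The rest of the protocol describes a different measurement for Phase One:

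- Section 3.1: the children are "aged between 12 to 36 months at the time of data collection".
- Section 3.2: the design is cross-sectional.
- Section 3.6.1: "data will be collected using a data collection form and the ASQs from 12 to 36 months of age on an Android tablet".
- Section 3.6.2, Aim 4a: the Aim 1 dataset, reused there as the comparator, is described as assessed at 12 to 36 months.
- Section 4, Phase One: "This is cross sectional data, and therefore any associations found are unable to assess causality".

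Section 3.6.2 (Aim 1) defines the primary outcome as the share of surviving participants with delay on at least one ASQ-3 domain and attaches no age to it. Section 3.6.4 itself lists the child's age when data were collected among the continuous variables to be summarised.

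**The concern.** A proportion with delay at age two is one quantity. A proportion with delay among children seen once, anywhere between 12 and 36 months, is another. The plan names the first and collects the second. If the share of children failing an ASQ domain changes over that age range, the pooled figure depends on the age mix of the children who were found and visited, and it should not be quoted as a two-year result.

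This concerns the primary outcome of Phase One, so it affects what the study may conclude. The dataset also stays in use as the comparator for Aim 4a, so an accurate description of it still matters although Section 2 reports Aim 1 as complete.

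**Working it through.** The plan gives no sample size, power or event count for Aim 1, so there is no figure to reproduce. The check compares the text and then asks when the pooled proportion and the two-year proportion agree.

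**1. What is measured.** The sections cited above give one assessment per child at 12 to 36 months, a range 24 months wide. Section 3.4 gives a discharge window of October 2011 to October 2013, also 24 months wide. A short survey of that cohort would therefore meet children spread over about two years of age, taking age as roughly equal to time since discharge. That is an assumption, as no length of stay is given. No section schedules a 24-month visit, sets a window around 24 months, or plans age standardisation or modelling.

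**2. How many children are near 24 months.** Assume ages are uniform over 12–36 months. The share within w months of 24 is 2w/24:

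| w (months) | Share |
|---|---|
| 1 | 2/24 = 8% |
| 2 | 4/24 = 17% |
| 3 | 6/24 = 25% |

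**3. When the pooled figure equals the two-year figure.** Let p(a) be the prevalence of delay at age a. The pooled proportion is the mean of p(a) over the ages in the sample. It is sure to equal p(24) in two cases:

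- p(a) is constant over 12–36 months; or
- p(a) is linear in a and the mean age is 24 months, since the mean of a linear function is its value at the mean age.

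The plan assumes, tests or reports neither condition.

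**4. Illustration with invented rates.** Take p(a) = p12 + (p36 − p12)(a − 12)/24, where p12 and p36 are the prevalences at 12 and 36 months. The documents supply no rates, so these show only the mechanism, in either direction.

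| p12 to p36 | Pooled, mean age 18 | p(24) | Pooled, mean age 30 |
|---|---|---|---|
| 30% to 50% | 35% | 40% | 45% |
| 50% to 50% | 50% | 50% | 50% |
| 60% to 30% | 52.5% | 45% | 37.5% |

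**5. Precision of age-specific figures.** The 95% half-width is 1.96 × √(p(1 − p)/n), at p = 0.5. For n, the only figure available is the 120 in the Section 6.3 incentives line. It is uncertain: 150 × 120 = 18,000, while the line shows 180,000. Taking 120 as an assumption:

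- all 120 children: 1.96 × √(0.25/120) = 0.089, about 9 points;
- each half of the age range, 60 children: 1.96 × √(0.25/60) = 0.127, about 13 points;
- only those within 3 months of 24 months, 30 children: 1.96 × √(0.25/30) = 0.179, about 18 points.

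**The case against.** The best defence is that two years is the midpoint of 12–36 months and is loose shorthand for a typical age. The formal outcome definition carries no age, the planned statistic is a plain proportion whatever it is called, and the mean and SD of age will be reported. ASQ forms are scored by age group, which reduces dependence on age. Aim 1 is descriptive and complete. Most of this stands, and it limits the severity. It does not make the label correct: age-specific forms do not guarantee equal failure rates across ages, and a mean age alone does not turn a pooled proportion into a value at 24 months.

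Four stronger readings are tempting, and the documents do not support them.

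- *No child's two-year status is measured.* Some children will happen to be near 24 months. The point concerns the pooled estimate.
- *Nothing sets the 12–36 month range.* Section 3.5.1 has no age-at-visit rule, but Sections 3.1 and 3.6.1 state the range.
- *The timeline implies visits well outside that range.* The Phase One table in Section 6.2 does not show which activity belongs to which period, and its columns are out of date order, so it cannot date the visits. The Section 6.3 budget provides data-collector meals for 15 days, which suggests a short survey.
- *The label biases Aim 4a.* Sections 2 and 3.6.2 describe that comparator correctly as 12–36 months, and the Aim 4a analysis never calls it a two-year outcome. Any age imbalance between the two Aim 4a groups would be a separate question.

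**Conclusion.** The inconsistency is real and lies in the current text. Section 3.6.4 names a two-year outcome, while the design delivers the prevalence of delay at 12 to 36 months from a single assessment. On an even spread of ages, about a quarter of children would be within three months of 24 months. That share rests on the assumed spread.

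The documents do not show that delay varies with age in this population, so neither the direction nor the size of any gap from a true two-year figure can be stated.

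Severity is minor to moderate. The design is declared and coherent, and no test or sample size depends on the label. But the label governs how the primary result will be read.

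**What to change.** In Section 3.6.4, Aim 1, replace the two-year wording in both sentences with: *at 12–36 months of age, at a single home visit*. Beside the pooled proportion, report the age distribution and the proportion with delay at 12–23 and at 24–36 months, using the age variable already listed.

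An estimate at 24 months from a logistic model on age is optional. It is likely to be imprecise, since Section 2 says Aim 2 was dropped because of the small sample. Changing the Section 3.5.1 criteria would serve no purpose now that Aim 1 is complete.

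The cost is a wording change and one re-tabulation of data already held. The downside is wider intervals for the age-specific figures: about 13 points either side instead of 9, under the assumed 120 children split evenly.

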Improved quality of care can help reduce this burden. In Rwanda, up to 40% of under- five deaths occur within the first 28 days (Rwanda DHS 2010), and approximately 6% of all neonates born are low birth weight (WHO-ECDD 2012) with prematurity ranking among the top causes of under-five mortality (Rwanda Health Statistics, 2012). Currently, these infants are discharged from hospitals with little support out in the community.

To address this gap, Partners In Health, in close partnership with the Rwanda Ministry of Health and technical support from Boston Children's Hospital and UNICEF, is designing and implementing a Pediatric Development Clinic (PDC) specifically dedicated to the nutritional, medical and developmental concerns of this high-risk population, with the goal of improving the quality of life for affected infants and children. However, there is a lack of data regarding the current outcomes of these vulnerable newborns in resource-limited settings (Ballot et al, 2012).

The proposed study aims to assess the baseline needs and disease burden of low birth weight and preterm infants, whom will routinely be evaluated in this clinic and will comprise a large majority of the clinic patients. These data will be used to inform the development and implementation of a pediatric developmental clinic (PDC) to follow these infants long-term, with the goal of improving overall pediatric health especially for those high-risk children. Following 1-2 years of implementation, an evaluation of clinical, nutritional and developmental outcomes of children followed in PDC will be conducted in comparison with the baseline study outcomes. Additionally, the evaluation of PDC will continue after initial post-assessments focusing on research on patient and provider experiences, overall clinic processes, quality of care, cost of the PDC model, PDC training and mentorship, expansion of the PDC model, and longer term outcomes to further help refine the PDC model.

2. Aims of the study:

Phase One: Baseline/Pre-PDC

Aim 1: To describe the baseline outcomes of a selected sample of infants discharged from a rural hospital neonatal unit. This aim has been completed.

Aim 2: To identify specific patient-level predictors of developmental delay (if we have sufficient power based on prevalence of developmental delay in the sample population). This aim will not be completed due to the small sample size.

Phase Two: Post-PDC

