Aim 3: To describe the pediatric development clinic (PDC) implementation process after approximately 24 months of implementation in terms of: services provided, referral system, patient population served and clinical, nutritional, and developmental status.

This aim has been completed.

Aim 4: To describe the clinical, nutritional, and developmental outcomes of vulnerable patients enrolled in PDC in comparison with:

- a) Medically vulnerable infants who did not receive PDC support from Phase One of this study. This comparison will be made using a cohort of preterm/LBW children who were born in Rwinkwavu District Hospital (RDH) before PDC started with medical, nutritional and developmental outcomes assessed at 12-36 months of age. under way
- b) The general population of rural Rwandan children. This comparison will be looking at developmental outcomes of children followed in PDC compared to the same age children from the general population using UNICEF data that was collected in under 5 children.¹

Phase Three: Expanding PDC

Aim 5: To evaluate the implementation of PDC during expansion, including patient characteristics, provider experiences, quality of care, impact of quality improvement interventions, cost-effectiveness, patient experiences, and patient outcomes. Findings from this aim will be used for continuous quality improvement of the PDC and informing scale-up.

Aim 5. 1. To evaluate the implementation of interventions that promote breastfeeding from as early as day one of life among newborns in the referring hospital neonatal units.

¹ The UNICEF data was conducted as part of an evaluation for UNICEF and Imbuto Foundation's ECD&F Baseline. PI of this study [name] and Co-I [name] were both on the UNICEF ECD&F study team and have access to the study data. The ECD&F study was approved by RNEC (PIs [name] and [name]).

3. Methods

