3.2. Study design

Pre-PDC Phase One:

The first phase is a **cross-sectional study** of infants discharged from a district hospital unit using caregiver report of medical and developmental outcomes as well as relying on measured growth parameters for nutritional status. This study will serve as a baseline of developmental, medical, and nutritional outcomes for comparison to similar children who received services from the PDC.

Post-PDC Phase Two:

All under 5 years of age, high risk (preterm, LBW) children enrolled in PDC since April, 2014 when PDC was initiated. The second phase will be a second cross-section of children who have been receiving services from the PDC from April 2014 when the clinic launched until present. The study will describe PDC implementation, demographic characteristics, and clinical, nutritional and developmental outcomes of all children from zero to five years of age enrolled in PDC from April 2014 to the time of study.

Post-PDC Phase Three:

This phase will use mixed methods, with data sources including routinely collected data, chart review, household data collection, focus groups and interviews to evaluate the PDC as it expands to new areas. The study will provide essential information of the feasibility of the PDC model at larger scale. The study will describe barriers to care, retention, long-term patient outcomes, and provider and patient experiences, quality of care delivered in the PDC especially on growth monitoring and developmental screening and costing of the PDC.

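### Aim 4a compares PDC children with a historical group by unadjusted tests, and its only regression does not assure a case-mix-adjusted PDC estimate

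*Combined protocol and SAP*

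**What the plan says.** The Aim 4a part of Section 3.6.4 (Analysis Plan) sets the comparison: "We will use bivariate analyses to compare the outcomes of infants who received PDC services with those who did not receive these services". Delay is binary (one or more failed ASQ-3 domains) and is tested by chi-square or Fisher. The same tests are named for nutritional and medical outcomes.

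One regression follows: "If we have sufficient power, we will conduct logistic regression analyses to look at predictors of developmental delay in the sample". No power threshold is given. The selection rule is: "Using backwards selection, all variables associated with developmental delay at $p < 0.10$ in bivariate will be included in the full model". PDC group is not named as a term in that model.

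The comparator is historical. Section 3.4 says of Phase One that "children were included if they were discharged between October 2011-October 2013 (prior to PDC implementation"; Section 2 describes its "medical, nutritional and developmental outcomes assessed at 12-36 months of age". Section 3.2 describes the Phase Two group as "children enrolled in PDC since April, 2014 when PDC was initiated" and under 5 years of age. Section 3.5.4 states that there is no randomisation. Sections 3.5.1 and 3.5.2 restrict Aim 4a to preterm and/or under-2000 g infants, with the Phase One exclusions.

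Two other places bear on this. Aim 2 was also a power-conditional regression, on the Phase One data, and Section 2 now says "This aim will not be completed due to the small sample size". For Phase One, Section 3.6.4 also lists what was recorded: "Continuous variables are birth weight, gestational age, age at the time of data collection, and household size", with sex, ubudehe category and caregiver education among the categorical variables.

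**The concern.** With a non-randomised, non-concurrent comparator, a crude difference mixes any PDC difference with differences in who the children are. The plan itself names likely sources. Under Aim 2 it expects birth-weight band, gestational-age band and malnutrition to be associated with delay, and Section 3.6.2 lists sector, sex, ubudehe, household size and education as potential confounders. That list is attached only to Aim 2, which was abandoned, and is not carried into Aim 4a.

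Remaining imbalance could make PDC look harmful or beneficial, or hide a real difference. The regression is not a dependable safeguard. It may not be run, it does not cover nutritional or medical outcomes, and if PDC group is one of the screened candidates, the confounding that hides a difference in the crude test can also remove PDC from the model.

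**Working it through.** **Is an adjusted Aim 4a estimate promised anywhere?** The main tests are bivariate. The regression is conditional, limited to delay and framed around predictors. The only other mention of multivariate analysis outside Aim 2, used as appropriate, belongs to Aim 5. So none is promised.

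**Does restriction settle it?** Infants under 37 weeks and/or under 2000 g can still differ in birth weight, gestational age, age at assessment and economic status. The minimum of 12 months since PDC enrolment matches the lower end of the 12-36 month baseline range, but no upper age limit is stated for the Aim 4a PDC group. Age-specific ASQ forms and z-scores standardise for age only in part.

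**How large could the effect be?** There is no stated figure to reproduce: the plan gives no group sizes, rates, alpha or power for Aim 4a. All inputs below are assumptions: 120 per group, one binary risk factor, delay of 30% (lower risk) or 60% (higher risk), no PDC effect, two-sided 5% test.

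Crude rate = 0.30 × (1 − s) + 0.60 × s, where s is the higher-risk share.
- Baseline, s = 0.25: 0.225 + 0.150 = 0.375.
- PDC, s = 0.35, 0.45, 0.55: 0.405, 0.435, 0.465.
- False difference: 3, 6, 9 points.

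Normal check for the middle case: SE = √[(0.375 × 0.625 + 0.435 × 0.565)/120] = 0.0633. Then 0.06/0.0633 = 0.95, and P(|Z + 0.95| > 1.96) ≈ 0.16.

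Simulated rejection rates (20,000 studies per scenario; uncorrected Pearson test against a logistic model with PDC forced in, the recorded risk factor and five null covariates):

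| Higher-risk share, baseline vs PDC | Crude | Adjusted, no error | 10% misclassified | 20% misclassified |
|---|---|---|---|---|
| 25% vs 35% | 8.3% | 5.4% | 5.8% | 6.6% |
| 25% vs 45% | 16.4% | 5.5% | 7.2% | 10.1% |
| 25% vs 55% | 29.8% | 5.0% | 8.9% | 16.0% |

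At 60 per group crude rejection is 6% to 17%. At 200 per group it is 9% to 44%, and the worst adjusted cases are 11% (10% misclassified) and 23% (20% misclassified). Reversing the imbalance (45% vs 25%) gives 16% crude rejection, nearly all falsely favouring PDC.

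**What would the p<0.10 screen do?** Assume a true odds ratio of 0.58, 120 per group, and that PDC group is screened like any other variable. With no imbalance, PDC fails the screen in about 43% of studies. With PDC infants sicker (25% vs 45%), it fails in about 77%. In that second case crude power is 14%, against 45%, 31% or 22% adjusted with 0, 10 or 20% misclassification. With no imbalance, crude and adjusted power are similar (44% and 46%).

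**Can the data carry the model?** At an assumed 240 children and 30-40% delay there are 72-96 events. Seven parameters (PDC plus six linear or binary covariates) give 72/7 = 10.3 to 96/7 = 13.7 events each. Using the plan's four birth-weight and three gestational-age bands adds three parameters: 72/10 = 7.2 to 96/10 = 9.6.

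**The case against.** The strongest reply is that Aim 4 is worded as description in comparison with other children, Section 4 says causality cannot be assessed, and eligibility and exclusions were aligned on purpose. All true, and it lowers the stakes. But the plan still tests for significant differences by PDC receipt, and a disclaimer does not correct a distorted contrast.

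The illustration is open to challenge. No document supports the 30%/60% risks, the size of the imbalance or its direction. Fisher's test, which the plan also allows, is more conservative: 6% to 25% at 120 per group in the same scenarios. In the mildest case with 20% misclassification, adjustment improves rejection only from 8.3% to 6.6%. These points stand.

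Some stronger readings are tempting but unsupported:
- That the regression will drop PDC. The plan does not say whether PDC group is screened or forced in, or whether the sample pools both groups. This is a gap in specification. Much of the 77% is also plain low power, since 43% occurs with no imbalance.
- That Aim 4a is the plan's only PDC contrast. Section 3.6.2 also lists the impact of PDC on child outcomes in Kirehe.
- That PDC children were assessed at older ages. On the Phase Two timetable (to May 2016), a child enrolled at birth in April 2014 would reach 25 months, inside the baseline range. The fair point is only that no upper limit is written down.
- That the Aim 2 outcome settles Aim 4a. The pooled Aim 4a sample is larger than Phase One alone; Aim 2 shows only that such a condition can fail.

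**Conclusion.** The point holds as a gap in the analysis plan that should be fixed. Aim 4a as written yields unadjusted comparisons for all its outcomes and does not assure an adjusted PDC estimate for any of them. That conclusion rests on the text alone.

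The size is illustrative. Under the assumptions above, crude rejection at a nominal 5% is 8% to 30% at 120 per group, in whichever direction the imbalance runs. Adjustment brings this to about 5% with an error-free covariate and 6% to 16% with 10-20% misclassification, or up to about 23% at 200 per group. Adjustment therefore reduces the bias without abolishing it. A reader might infer that the Aim 4a result is known to be biased, or biased against PDC; the documents give no case-mix data to support either.

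**What to change.** Make the main Aim 4a estimate the PDC-group odds ratio with 95% confidence interval from one pre-specified logistic model.
- Force PDC group in, with a short fixed covariate set available in both datasets: age at assessment, sex, birth weight, gestational age, caregiver education and one economic measure. Confirm that the economic measure is common: Phase One lists ubudehe, while Aim 4 lists a DHS wealth index.
- Report it whatever the power. If events are sparse, which is likely if covariates are banded, use a penalised or propensity-score version.
- Do the same for the binary nutritional and medical outcomes where events allow.
- Drop the p<0.10 screen and backwards selection for this contrast, and keep chi-square/Fisher as unadjusted description.
- Restrict both groups to 12-36 months at assessment.
- State how missing covariates are handled, since Section 4 expects missing values.
- Add to the limitations that calendar period coincides with group and cannot be adjusted away, and that misclassified gestational age or birth weight leaves residual confounding.
- Because Section 2 marks Aim 4a as under way, fix the model before group results are seen, or label it post hoc.

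The cost is plan wording, modest analyst time, some loss to missing covariates and slightly wider intervals. Standard errors on the log-odds scale were about 3-16% larger in the simulation, which had no missing data.
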